### 9.1.2 Assessment for 3D Volumetric Loss

The 3D [REDACTED] system will be used to obtain a 360° stitched image of the body. The system is composed of a 3D stereoscopic camera, tripod, and a turntable that gently rotates, stopping at one-eighth increments (45° angle rotation), to obtain 8 images of the body. The 8 images are then reconstructed to obtain a 360° image of the body and allowing quantification of the abdomen and flank areas.

To obtain optimal results, proper subject conditioning, camera orientation using the tripod, room organization, and standard backgrounds are all critical to minimize volume variations due to natural variability of the anatomy. In addition, each site will be provided with a detailed Image Procedure document, a training video, on-site training, and qualifications to ensure strict adherence to the imaging aspects of the study.

A [REDACTED] camera will acquire a 3D representation of the anatomical surface of the body. The skin surface is “textured” and the color and intensity patterns on its surface enable the stereoscopic 3D reconstruction methods to be applied.

[REDACTED] matching technology uses a 2-step matching algorithm process. First, the baseline and post-treatment images are matched to the overall global area. Next, to quantify the volume variation, a trained technician defines a Region of Interest on the baseline surface, defined as a cylinder on the shape of the 3D contour. The defined cylinder enclosed on the baseline surface and the follow-up surface on the other side is used to determine the actual volume.

The volume change is provided in cubic centimeters (cc) units and is illustrated by an Elevation Color Map. The following color codes are used to indicate the magnitude of volume change: gray is no change, smaller negative volumes in light blue, larger negative volumes in dark blue, smaller positive volumes in yellow, and larger positive volumes in red.

## **9.2 Safety Assessments**

### **9.2.1 Adverse Events**

Throughout the course of the study, all AEs will be reported and monitored on an AE CRF, including event name, duration, seriousness, relatedness, severity, action taken, and outcome. If AEs occur, the first concern will be the safety of the study participants.

All events and device deficiencies are to be recorded on the corresponding CRF for the patient upon the site becoming aware of said event.

AEs will be collected throughout the study once there is a signed ICF. At each visit, the investigator or designated study staff will solicit and assess the patient for AEs. Previously recorded AEs and changes in therapy/concomitant medications are to be updated as necessary. All reportable AEs and clinically significant abnormal laboratory findings will be documented on the appropriate electronic CRF (eCRF).

#### **Adverse Event Definition**

An AE is defined in accordance with International Organization for Standardization (ISO) 14155 as any untoward medical occurrence, unintended disease or injury, or untoward clinical signs (including abnormal laboratory findings) in subjects, users, or other persons, if related to the investigational medical device. This definition includes events related to the investigational medical device or comparator and events related to the procedures involved. Disease signs and symptoms that existed before the study treatment are not considered AEs unless the condition recurs after the participant has recovered from the pre-existing condition or the condition worsens in intensity or frequency during the study.

AEs will be monitored throughout the study once the subject has signed the informed consent form. At each post-baseline visit, the investigator will begin querying for AEs by asking each participant a general, non-directed question such as “Have you had any changes to your condition since your last visit?” Previous AEs and changes in therapy/concomitant medications are to be updated. Directed questioning and examination will then be done as appropriate. All reportable AEs and clinically significant abnormal laboratory findings will be documented on the appropriate eCRF.

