### **Anticipated Device Effects**

These are known effects of the CoolSculpting Procedure, previously recorded in prior studies as transient and/or temporary effects related to the cold application and/or vacuum pressure inherent in the treatment. Anticipated effects of the device which will not be considered AEs include:

- inflammation of the subcutaneous fat layer, which is a desired effect of the procedure;
- sensations of coldness, stinging, burning, pinching, or pressure associated with placement of the applicator and the initiation of the cold treatment;
- known skin effects (eg, blanching; erythema, bruising, purpura, petechiae, swelling, discomfort, tenderness, or soreness at the treatment site, all mild to moderate in nature), which are temporary effects that resolve spontaneously shortly after the procedure; and
- localized sensory changes (eg, numbness, tingling) at the treatment area resolving within 12 weeks of the procedure.

If the severity of these anticipated effects causes disruption to the subject's daily activities, then they will be evaluated as a potential adverse effect.

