Gastrointestinal Symptoms	Nausea, bloating, or diarrhea temporally related to the procedure (within the first few hours after the procedure).
Contour Irregularity	Significant indentation or contour irregularity in the treatment area that would require surgical intervention.
Allergic/Irritant Contact Dermatitis	Itchy rashes and skin peeling that may result from prolonged exposure to gel pad or applicator pressure.
Subcutaneous Induration	Hardness within the treatment area, either as general firmness or discrete nodules.
Paradoxical Hyperplasia	Visibly enlarged tissue volume within the treatment area which may develop 2-5 months after treatment.
Hernia	Creation or exacerbation of hernia. Hernia is defined as a protrusion of an organ or the fascia of an organ through the wall of the cavity that normally contains it.
Other	Any other untoward medical event determined by the investigator to be an AE, regardless of the relationship to the device or treatment.

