## Secondary Endpoints

All secondary endpoints will be measured at Week 12 for subjects who receive 1 treatment session and at Week 20 for subjects who receive 2 treatment sessions, except for AEs, which will be assessed for all scheduled visits. The analyses on the secondary endpoints will include:

1. Proportion of subjects by treated area(s) (abdomen alone, flanks alone, and both abdomen and flanks) with “satisfied” or “very satisfied” on CSQ Item #1.
2. Proportion of subjects by number of treatment cycles who receive 1 or 2 treatment sessions with “satisfied” or “very satisfied” on CSQ Item #1.
3. Proportion of subjects by BMI categories with “Satisfied” or “Very Satisfied” on CSQ Item #1.
4. Mean change in volume of fat from baseline as measured by 3D photography.
5. Frequency of AEs including SAEs; and ADEs including SADEs.

[REDACTED]

[REDACTED]

[REDACTED]

[REDACTED]

[REDACTED]

[REDACTED]

[REDACTED]

[REDACTED]

[REDACTED]

[REDACTED]

[REDACTED]

[REDACTED]

[REDACTED]

[REDACTED]

[REDACTED]

[figure not shown]
All individual items and the total score are transformed to a 0 (no impact) to 100 (highest impact) point scale.

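### Read literally, the protocol's only AE definition limits AEs and SAEs in subjects to device- or procedure-related events, which contradicts its own causality and reporting rules

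*Protocol*

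**What the plan says.** The protocol has one AE definition, in Section 9.2.1 under Adverse Event Definition. It covers untoward medical occurrences, unintended disease or injury, and untoward clinical signs "in subjects, users, or other persons, if related to the investigational medical device". The sentence after it reads "This definition includes events related to the investigational medical device or comparator and events related to the procedures involved". Nothing there says that unrelated events also count. Section 9.2.1.1 defines an SAE as an AE meeting a seriousness criterion, so any limit on AEs passes to SAEs.

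Secondary endpoint 5 (protocol 6.2) is "Frequency of AEs including SAEs; and ADEs including SADEs". The SAP has no AE definition of its own. Section 11.2 sends the reader to the protocol, citing Section 11.1. It then classifies an AE as an adverse device effect (ADE), or as procedure-related, when causality is graded possible, probable or causal. It tabulates treatment-emergent AEs (TEAEs), SAEs, ADEs, serious ADEs (SADEs) and procedure-related AEs separately.

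**The concern.** An AE definition decides what reaches the database. Here the relatedness condition closes a list that begins with subjects, so on its face it applies to them. A site that works from the definition could leave out an unrelated illness or hospital admission. A site that works from the causality or SAE reporting text would record it.

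About 8 sites in several countries take part, and SAP 12.1 tabulates TEAEs by site and country. If sites read the text differently, differences between them in AE frequency could reflect the reading and not safety. The SAP cannot settle the matter, because it defers to the protocol.

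**Working it through.** The plan gives no figure to reproduce. The check is to take the definition literally (AE in a subject = device-related or procedure-related) and test it against the other safety text.

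1. **Potential Adverse Effects table, protocol 5.2.1.2.** The last row admits "Any other untoward medical event determined by the investigator to be an AE, regardless of the relationship to the device or treatment". An event cannot be an AE regardless of relationship and also only if related. This is a direct conflict.

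2. **Assessment of Causality, protocol 9.2.1.** The investigator grades the relationship of the AE, if there is one, to the device and/or the study procedure. The scale has a Not related grade. Because the instruction covers device and procedure together, procedure-related AEs do not explain it away. Under the literal definition, no AE could be graded Not related to both. This is a conflict.

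3. **SAE reporting, protocol 9.2.1.1.** All SAEs from consent to the final visit go to the sponsor, and the case history must state whether each was or was not related to the device or procedure. Under the literal definition a negative answer on both counts could not arise. This is a conflict.

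4. **Text that favours the wider reading without contradicting the definition.** Section 9.2.1 says "All events and device deficiencies are to be recorded on the corresponding CRF for the patient" and makes relatedness a recorded item. The device-related AE has its own name and definition, the ADE, which would be largely redundant if nearly all AEs were already device-related.

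5. **Scope, by count.** These counts show which outputs depend directly on the definition. They are not an effect size.
   - Secondary endpoint 5: 2 of 4 event classes (AEs and SAEs; not ADEs or SADEs).
   - SAP 11.2 overall summary: 3 of 7 items depend directly (TEAEs, SAEs, TEAEs leading to discontinuation) and 3 do not (ADEs, SADEs, procedure-related AEs). Deaths cannot be placed, because their data source is not stated. 3 + 3 + 1 = 7.
   - SAP 11.2 tables by system organ class and preferred term: 4 of 8 (TEAEs; TEAEs by severity; treatment-emergent SAEs; TEAEs leading to discontinuation).
   - SAP 12.1 TEAE and ADE tables: 2 of 4 per subgroup. The Chinese and Asian subgroups also receive other safety summaries, which this count leaves out.

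6. **Indirect route to ADE counts.** Assessment of Causality places events whose relatedness cannot be assessed in the Possible grade. SAP 17.6 imputes missing causality as related for AEs starting on or after first treatment. If the definition decides whether such events are recorded at all, it can also move ADE counts slightly.

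7. **SAP 11.2 against the protocol, separately.** SAP 11.2 starts AE collection at the first treatment visit, while protocol 9.2.1 starts at signed consent. SAP 17.5 already handles AEs that began before first treatment, so the SAP is also at odds with itself. In addition, protocol Section 11.1 is Audit and Inspection; the AE definitions are in 9.2.1.

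**The case against.** The best defence is that the operating instructions settle the matter. All events go on the CRF, visits open with a general question that has no relatedness filter, all SAEs are reportable, and nothing tells a site to withhold an unrelated event. The condition can also be parsed as applying only to users and other persons, which removes the conflict. Most of this stands, and it is why data loss cannot be asserted. But these instructions show what was probably intended; they do not correct the definition, and no text confirms the looser parse.

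A reader might go further than the documents allow in four ways:

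- **That unrelated events will be lost or AE rates understated.** The recording instructions make this uncertain, and the documents give no basis for a size.
- **That SAP 11.2 contradicts the definition because it treats ADEs and procedure-related AEs as subsets.** Under the literal definition both remain valid subsets. The TEAE tables would then add little beyond them, but that is redundancy and not conflict.
- **That follow-up from consent is itself a contradiction.** The protocol says "AEs will be monitored throughout the study once the subject has signed the informed consent form", before any device exposure. However, the definition also covers procedure-related events, so early monitoring is compatible with it.
- **That ADEs, SADEs and procedure-related AEs are wholly unaffected.** This is too absolute, given how unassessable and missing causality are handled.

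**Conclusion.** The point holds as an internal contradiction, and confidence in that is high. The definition, read as written, cannot be reconciled with the last row of the potential adverse effects table, the causality assessment or the SAE case-history requirement. The AE and SAE part of secondary endpoint 5, and the TEAE and SAE tables, depend on which text a site follows. The primary endpoint is unaffected. ADE counts should be little affected, except for events with unassessable or missing causality.

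No effect size can be given. The conclusion rests on the literal parse, in which the condition attaches to the whole list including subjects, and on the documents' own wording; the ISO standard that the protocol cites was not used. The two SAP 11.2 discrepancies are real, but they have little or no effect on the TEAE tables: those exclude events confined to the pre-treatment period, and SAP 4.0 puts screening at no more than 7 days. Severity is minor.

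**What to change.** Amend the definition in protocol 9.2.1 so that, for study subjects, any untoward medical occurrence is an AE whether or not it is related to the device or procedure. Any relatedness condition should apply only to users or other persons. The SAE definition then needs no edit.

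Keep both existing exclusions: the list in protocol 5.2.1.2 introduced by "Anticipated effects of the device which will not be considered AEs include", with its provision for re-evaluating effects that disrupt daily activities, and the rule in 9.2.1 that "Disease signs and symptoms that existed before the study treatment are not considered AEs unless the condition recurs" or worsens. ADEs and procedure-related AEs can stay as subsets defined by causality grade.

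In SAP 11.2, start AE collection at signed consent and cite protocol Section 9.2.1 in place of 11.1.

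The cost is a one-sentence protocol amendment and two SAP wording edits. Sites may have slightly more to record, and the reported AE frequency may be higher.

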#### **Adverse Device Effect**

An ADE is defined in accordance with ISO 14155 as “an AE related to the use of an investigational medical device.” This definition includes any AEs resulting from insufficient or inadequate instructions for use, deployment, implantation, installation, or operation, or any malfunction of the investigational medical device as well as any event resulting from use error (per ISO 62366) or from intentional misuse of the investigational medical device.

---

## Device Deficiency or Complaints

A device deficiency is defined in accordance with ISO 14155 as inadequacy of a medical device including issues with respect to its identity, quality, durability, reliability, safety, or performance. Device deficiencies include malfunctions, use errors, and inadequate labelling.

If a device deficiency occurs, the investigator will notify Allergan using the CRF. Device deficiencies shall be documented throughout the study and appropriately managed by Allergan. The Clinical Trial Site will enter all the information regarding device deficiency into the appropriate CRFs. Allergan shall review all device deficiencies and determine and document in writing whether they could have led to a SADE. These shall be reported to the regulatory authorities and IRBs as required by Federal regulations.

## Assessment of Severity

Severity is a clinical determination of the intensity of an AE. The severity assessment for a clinical AE will be assigned a category by the investigator as follows:

Mild	An AE that is easily tolerated by the subject, causes minimal discomfort, may require only minimal treatment and does not interfere with everyday activities.
Moderate	An AE that is sufficiently discomforting to interfere with normal everyday activities; intervention may be needed, but poses no significant or permanent risk of harm.
Severe	An AE that prevents normal everyday activities; treatment or other intervention usually needed.

If there is a change in severity of an AE, it must be recorded as a separate event.

## Assessment of Causality

Relationship to a device refers to a determination of the relationship (if any) between an AE and the device. A causal relationship is present if the investigator determines that there is a reasonable possibility that the AE may have been caused by the device.

An AE could be considered procedure-related when, in the judgment of the investigator, it is reasonable to believe that the event is associated with the procedure, regardless of the relationship to the study device. Procedure-related causes that contribute to the occurrence of the event can be attributed to other products, surgical techniques, or medications required specifically for the procedure.

Every effort will be made by the investigator to assess the relationship of the AE, if any, to the device and/or study procedure. Causality should be assessed using the categories presented in the following table:

Not related	Clinical event of which the relationship to the device and/or procedure can be excluded, such as if the event is incompatible time relationship to study procedure and/or use of the device, involves a body part or organ not expected to be affected by the device or procedure, could be explained by underlying disease or other drugs or chemicals or is incontrovertibly not related to the study device, and is not due to use error.
Unlikely	Clinical event whose time relationship to use of the device and/or study procedure makes a causal connection improbable, but that could plausibly be explained by underlying disease or other drugs or chemicals.
Possible	Clinical event with a reasonable time relationship to the use of the device and/or study procedure, but that could also be explained by concurrent disease or other drugs or chemicals. Cases where relatedness cannot be assessed or no information has been obtained should also be classified as possible.
Probable	Clinical event with a reasonable time relationship to the use of the device and/or study procedure, and is unlikely to be attributed to concurrent disease or other drugs or chemicals.
Causal relationship	Clinical event with plausible time relationship to the use of the device and/or study procedure, is a known side effect of the product category the device belongs to or of similar devices and procedures; follows a known response pattern to the medical device; involves a body-site or organ that the device or procedures are applied to and/or influence; harm is due to error in use, and that cannot be explained by concurrent disease or other drugs or chemicals.

### Follow-up of Adverse Events

All investigators should follow up with subjects with AEs until the event is resolved or until, in the opinion of the investigator, the event is stabilized or determined to be chronic. Details of AE resolution must be documented in the CRF.

### Documentation and Reporting of Adverse Events

AEs should be reported and documented in accordance with the procedures outlined below. All AEs occurring during the study must be documented on the relevant CRF pages. The following data should be documented for each AE in the appropriate CRF fields:

- Description of the symptom event.
- Classification of ‘serious’ or ‘not serious.’
- Severity.
- Date of first occurrence and date of resolution (if applicable).
- Action taken.

- Causal relationship.
- Outcome of event.

### **9.2.1.1 Serious Adverse Events**

#### **Serious Adverse Event Definition**

An SAE is defined as an AE that:

- led to death
- led to serious deterioration in the health of the subject, that either resulted in:
  - a life-threatening illness or injury; or
  - a permanent impairment of a body structure or a body function, or
  - in-patient or prolonged hospitalization; or
  - medical or surgical intervention to prevent life-threatening illness or injury or permanent impairment to a body structure or a body function; or
  - if a subject becomes pregnant, then spontaneous abortion, fetal distress, fetal death, or a congenital abnormality or birth defect is considered an SAE

In addition, medical and scientific judgment is required to decide if prompt notification is required in situations other than those defined for SAEs above. This may include any event that the investigator regards as serious that did not strictly meet the criteria above but may have jeopardized the subject or required intervention to prevent one of the outcomes listed above, or that would suggest any significant hazard, contraindication, side effect, or precaution that may be associated with the use of the investigational product.

#### **Serious Adverse Device Effect (SADE)**

An ADE that resulted in a SAE or that might have led to any SAE consequences if a suitable action had not been taken or intervention had not been made.

All device or surgical related SAEs must be entered into the electronic data capture (EDC) system within 24 hours of being notified of the event. The sponsor will be notified by EDC system once the SAE electronic form has been submitted.

- The relationship of the clinical event to the devices and procedure should be reported on the Form and will be determined by the investigator.
- Following evaluation of each SAE, the responsible ethics committee will be notified as appropriate based on national regulations.

- All SAEs that occur from the time the ICF is signed through to their final study visit must be reported to the sponsor. In addition to entering the information into the EDC system, the investigator must:
  - Notify the sponsor immediately (within 24 hours) by emailing the Allergan Product Surveillance team at:  
[contact] using SAE form.

The following SAE information should be provided:

- Description of the symptom event (including treatment dates, areas treated, event description, etc.)
- Applicator(s) and Serial Number used during treatment
- Classification of ‘serious’ or ‘not serious’
- Severity
- Date of first occurrence and date of resolution (if applicable)
- Action taken
- Causal relationship
- Outcome of event Report as much information within 24 hours regardless of the amount of information available, although the investigator is expected to provide as much information as possible.

Obtain and maintain in his/her files all pertinent medical records, information, and medical judgments from colleagues who assisted in the treatment and follow-up of the subject.

Provide the sponsor with a complete, written case history (AE report form) that includes a statement as to whether the event was or was not related to the use of the investigational device or procedure.

The sponsor (or its representative) will report all SAEs associated with the use of the study device to the regulatory agencies (Ethics Committee, Competent Authorities) as appropriate according to relevant standard operating procedures and to the national laws of the country where the trial is performed.

In every SAE, appropriate measures should be taken to treat/resolve and monitor the subject. The investigator should keep Allergan closely informed of the progress as related to the SAE. Any subjects who are withdrawn from the study due to an AE shall still be followed until the outcome is resolved.

Details of the procedures to be followed if a pregnancy occurs are provided in [Section 7.3.4](#).

---

